- The correlation of Δ TUV_{global[5w]} and constituent parameters of Δ CDAI_{12/24w} and ACR_{12/24w} including:
 1. Tender Joint Count (TJC)
 2. Swollen Joint Count (SJC)
 3. Patient assessment of global disease activity
 4. Rheumatologist assessment of global disease activity
 5. Patient assessment of pain
 6. Patient assessment of physical function
 7. Acute-phase reactant value

Statistical Methods:

ARMS 1-2

Longitudinal precision and camera-specific precision will be analyzed with confidence intervals for Root Mean Square Difference (RMSD) and the mean difference (i.e., the bias) between the relevant time points. Confidence intervals (95% confidence level)

will be calculated using Normal theory results ([Lin 2002](#)). As a sensitivity measure, the 80th and 90th percentiles of the distribution of the absolute differences will be computed using quantile methods.

Stability of the mean/variance relationship will be assessed with a 95% confidence interval for the difference between the CV for RA and HC subjects at each time point. If the CV for both groups at an imaging time point is less than 0.30, a 95% confidence interval based on the methods outlined in ([Forkman 2009](#)) will be provided. Because Forkman's methods are based on Normal theory, a 95% bootstrap confidence interval will also be provided for all time points.

Temporal stability of the 150 mcg dose will be assessed with a 95% Student's T interval for the difference between the TUV at 60 minutes and at 180 minutes. As a sensitivity check, a signed-rank test of the hypotheses:

$$\begin{aligned} H_0: \mu_{180} - \mu_{60} &= 0 \\ H_1: \mu_{180} - \mu_{60} &\neq 0 \end{aligned}$$

where μ_{180} represents the median TUV at 180 minutes and μ_{60} represents the median TUV at 60 minutes, will be provided.

ARM 1

Normal ranges in HC subjects will be estimated by pooling similar joints and computing the average TUV per joint per subject. The 5 and 95 percentiles will be estimated using quantile regression methods. Joints to be pooled include the following:

- Shoulders (bilateral, 2 per subject)
- Knees (bilateral, 2 per subject)
- Wrists (bilateral, 2 per subject)
- MCP (bilateral, 5 per hand, 10 per subject)
- PIP (bilateral, 5 per hand, 10 per subject)

ARM 2

The qualitative evaluations of SPECT/CT in detecting localization within synovial spaces of the bilateral hands and wrists.

ARM 3

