2.2 Secondary Objective(s)

- To assess the temporal post-injection stability of TUV_{joint} and TUV_{global} at a dose of 150 mcg tilmanocept radiolabeled with 10 mCi of Tc 99m.
- To establish normal ranges for TUV_{joint} in HCs.
- To assess Tc 99m tilmanocept anatomic localization based on SPECT/CT imaging of the synovial space in hands and wrists

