4.1.2 Secondary efficacy variables

- Qualitative evaluations of SPECT/CT image detecting localization of Tc 99m tilmanocept in the synovial spaces of the bilateral hands and wrists. (Arm 2 only).
- CDAI score at baseline (CDAI_{0w}), 12 (CDAI_{12w}) and 24 weeks (CDAI_{24w}) (Arm 3 only).
- ACR Response Criteria at 12 and 24 weeks (Arm 3 only).
- Constituent scores of the ACR Response Criteria at baseline, 12 weeks, and 24 weeks, including:
 - TJC
 - SJC
 - Patient assessment of global disease activity
 - Rheumatologist assessment of global disease activity
 - Patient assessment of pain
 - Patient assessment of physical function
 - Acute-phase reactant value.
- Constituent scores of the CDAI score
 - TJC
 - SJC
 - Patient Global Assessment
 - Physician Global Assessment.

The secondary efficacy endpoints for this study are:

ARMS 1-2

- The temporal stability of TUV_{joint} and TUV_{global} using a 150 mcg tilmanocept mass dose/10 mCi radiolabeling dose, which is defined as the squared difference between the 1-hour and 3-hour planar images. (This endpoint was analyzed to the sponsor's satisfaction in IA-3.)

ARM 1

- The normal upper limit of TUV_{joint} in HC subjects, which is defined the upper limit of a 95% prediction interval at 60 ±15 minutes:
 - TUV_{joint} of evaluated joints (i.e., wrists, MCPs, PIPs, knees, elbows, shoulders in Arms 1 and 2, and wrists, MCPs, and PIPs in Arm 3).

ARM 2

- The qualitative evaluations of SPECT/CT in detecting localization within synovial spaces of the bilateral hands and wrists.

ARM 3

- $\text{TUV}_{\text{global}[0w]}$ and response to new anti-TNF α bDMARD therapy defined by the change from baseline (CFB) of CDAI to 12 ± 1 weeks and 24 ± 1 weeks (ΔCDAI_{12w} and ΔCDAI_{24w} , respectively) and by the changes from baseline in each of the ACR Response Criteria components at 12 (± 1) weeks and at 24 (± 1) weeks.
- $\Delta\text{TUV}_{\text{global}[5w]}$ and response to new anti-TNF α bDMARD therapy defined by the CFB of CDAI to 12 ± 1 weeks and 24 ± 1 weeks (ΔCDAI_{12w} and ΔCDAI_{24w} , respectively).
- $\Delta\text{TUV}_{\text{global}[12w]}$ and $\Delta\text{TUV}_{\text{global}[24w]}$.

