4.2.2 Secondary Efficacy Variables

Secondary Endpoints for Arm 1 only

The normal ranges of TUV_{joint} will be estimated from data collected from healthy subjects (study arm 1) at 60 minutes post-injection. The mean, standard deviation, n (number of joints), and quantile regression estimates of the 5 and 95 percentiles will be provided for shoulder, elbow, wrist, MCP, PIP, and knee. All joints will be summarized individually.

Secondary Endpoints for Arms 1 and 2

The temporal quantitative stability of the images will be assessed by computing the fraction of observations for which $|\Delta TUV_{global}| \leq 0.075$ for the difference between the 60 and 180 minute images. The hypotheses

$$H_0: \pi \leq 0.80$$

vs

$$H_a: \pi > 0.80,$$

where π represent the fraction of unsigned differences less than 7.5% will be tested with an exact test and a Clopper-Pearson (exact) 95% confidence interval for p will be provided. The RMSD will be analyzed by joint, providing 95% confidence intervals for the RMSD using both Normal theory methods and a bootstrap estimate with 5000 bootstrap replications.

The 80th and 90th percentiles of the distribution of unsigned differences will be estimated using quantal regression methods. (These analyses were completed to the sponsor's satisfaction in IA-3.)

Secondary Endpoint for Arm 2 only

Qualitative evaluations of SPECT/CT imaging in localizing tilmanocept uptake will be estimated from the active RA subjects (Arm 2 only) on the joints of the hands and wrists. A frequency table of counts and percent of subjects will be provided.

Secondary Endpoints for Arm 3 only

All RA quantitative assessment variables (CDAI, ACR Response Criteria component scores, DAS28 score, and HAQ-DI) will be summarized by arm, computing the mean, standard deviation, number of observations, minimum, median, and maximum for the observed values at each time point and for the change from baseline for values collected after Day 0. The ACR Response Criteria will be summarized with a frequency table of the highest ACR Response level (None, ACR20, ACR50, ACR70) attained by that subject at that time point. That is, a subject who satisfies ACR50 also satisfies ACR20 but will not appear in the frequency count for ACR20.

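### The SAP drops the protocol's T interval and signed-rank test for the 60 versus 180 minute TUV difference, so systematic drift is described but has neither an interval nor a test

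*SAP*

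**What the plan says.** **Objective.** Protocol 2.2 lists "To assess the temporal post-injection stability of TUV", for both the joint and the global measure, as a secondary objective.

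**Protocol method.** The synopsis (Statistical Methods, Arms 1-2) says temporal stability "will be assessed with a 95% Student's T interval for the difference between the TUV at 60 minutes and at 180 minutes". It adds "As a sensitivity check, a signed-rank test of the hypotheses" of zero versus non-zero difference between 180 and 60 minutes. Protocol 9.5.3.2, on secondary endpoints for Arms 1-2, gives no temporal-stability method, so the synopsis is the protocol's only statement of one.

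**SAP definition.** SAP 4.1.2 gives the temporal-stability endpoint for Arms 1-2, "which is defined as the squared difference between the 1-hour and 3-hour planar images". No acceptance limit is attached.

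**SAP analysis.** SAP 4.2.2 says "The temporal quantitative stability of the images will be assessed by computing the fraction of observations for which" the absolute change in TUV_global does not exceed 0.075. It sets H0: π ≤ 0.80 against Ha: π > 0.80, where π is said to "represent the fraction of unsigned differences less than 7.5% will be tested with an exact test", with a Clopper-Pearson interval. It adds: "The RMSD will be analyzed by joint, providing 95% confidence intervals for the RMSD". It also asks for the 80th and 90th percentiles of the unsigned differences.

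**What else the SAP keeps.** SAP 4.2.1 summarises signed differences (mean, SD, n, minimum, median, maximum) for the 60 versus 180 minute A scans, for all assessed joints and TUV_global.

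**Status.** The SAP introduction states consistency with Amendment 4. SAP 4.1.2 and 4.2.2 say this work was completed to the sponsor's satisfaction in interim analysis 3. The SAP 7.0 table list has no table for 60 versus 180 minutes.

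**The concern.** The planned measures answer different questions. The mean signed difference estimates drift: whether TUV moves systematically between one and three hours. The fraction within a limit, and the RMSD, measure agreement, in which drift and scatter are combined. Protocol 3.1.1.3 gives as one reason for the two-hour comparison the possibility of pharmacokinetic effects that depend on time, which is a question about drift.

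The protocol attached an interval and a sensitivity test to that question. The SAP removes both without saying so. Its only formal test for this endpoint is an agreement test on TUV_global, although the objective also names the joint measure. A report could therefore state that TUV passed its stability test while every subject's value had moved the same way, with no confidence interval to show how far. The endpoint bears on whether 1-hour and 3-hour imaging are interchangeable, and Protocol 9.4 and SAP 1.3 give temporal stability as the purpose of Arm 1's sample size.

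**Working it through.** **1. Inputs from the documents.** n = 38 evaluable per arm (SAP 1.3); limit 7.5% and null fraction 0.80 (SAP 4.2.2); 95% T interval (protocol synopsis).

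**2. Assumptions.** The documents give no alpha for the exact test, so one-sided 5% and 2.5% are both shown. Paired differences are taken as normal and in percent of TUV, with mean μ (drift) and SD σ (scatter). The values of μ and σ are illustrative.

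**3. The plan's own figure.** No sample size calculation is given for temporal stability. SAP 1.3 states 80% power for Arm 2 under the same pair of hypotheses, but gives neither alpha nor the alternative π, so N = 38 can only be solved backwards.

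| One-sided level | Pass rule | Exact alpha | π giving 80% power |
|---|---|---|---|
| 5% | ≥ 35 of 38 | 0.0387 | 0.939 |
| 2.5% | ≥ 36 of 38 | 0.0113 | 0.959 |

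**4. Formulas.**
- Share within the limit: π = Φ((7.5 − μ)/σ) − Φ((−7.5 − μ)/σ).
- Chance that the fraction test passes: P(Bin(38, π) ≥ 35) or P(Bin(38, π) ≥ 36).
- T interval half-width when the sample SD equals σ: t(0.975, 37 df) × σ/√38, with t = 2.026.

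**5. Main example, μ = +4, σ = 2.**
- π = Φ(1.75) − Φ(−5.75) = 0.960.
- The fraction test passes with probability 0.935 at the 5% level and 0.806 at the 2.5% level.
- Half-width = 2.026 × 2/6.164 = 0.66, so a sample mean of 4 gives an interval of about 3.3% to 4.7%. The noncentrality is 4/(2/6.164) = 12.3, and the interval excludes zero in more than 99.9% of trials.

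**6. Other values.**

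| Drift μ (%) | SD σ (%) | π | Passes at 5% | Passes at 2.5% | T interval contains 0 |
|---|---|---|---|---|---|
| +4 | 2 | 0.960 | 94% | 81% | < 0.1% |
| +3 | 2.5 | 0.964 | 95% | 84% | < 0.1% |
| +3 | 2 | 0.988 | 99.9% | 98.9% | about 0% |
| 0 | 3 | 0.988 | 99.9% | about 98.9% | 95% |
| 0 | 7.5 | 0.683 | 0.05% | < 0.01% | 95% |

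Rows 3 and 4 show the gap. A uniform 3% shift and no shift at all give the same share within the limit and the same pass rate; only the mean signed difference separates them. Row 5 shows the converse: the T interval alone would not reveal that 32% of subjects moved by more than 7.5%. Neither measure replaces the other.

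**7. Squared difference.** Its expectation is μ² + σ², so it also combines the two. Drift 0 with SD 6 gives 36; drift 5.66 with SD 2 gives 32.04 + 4 = 36.04.

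**The case against.** **Drift is already summarised.** This stands. SAP 4.2.1 requires the mean, SD and n of the signed A-scan differences, for joints and TUV_global, and a T interval can be calculated from those three numbers. A reader might infer that the SAP conceals drift; it does not. What is missing is the planned interval, the signed-rank test and an explanation.

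**Three rival definitions giving opposite verdicts.** A reader might infer this, but the documents do not support it. The squared difference has no acceptance limit, and it is the term inside the RMSD that SAP 2.5 and 4.2.2 already plan, so it is loose wording more than a competing method. The protocol sets no rule that an interval covering zero means stable; a zero null appears only in its signed-rank check. The fraction test is the only one of the three measures with a pass criterion.

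**Agreement may be the better criterion for interchangeability.** This also stands. The synopsis describes a two-hour window meant to suit clinical workflow, and Protocol 3.1.1.3 goes on to speak of overall stability, which includes scatter. With no drift, the T interval covers zero in 95% of trials whatever the SD. A reader might conclude that the 7.5% test should be demoted and stability judged on the T interval; the documents do not support that, and it would be a poor exchange.

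**Interim analysis 3.** The interim analysis plan is not among the documents, so it may have included the T interval. That is unknown. The SAP's remark about the sponsor's satisfaction names no measure.

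**Conclusion.** The point holds as an unexplained departure from the protocol on a secondary endpoint. The SAP omits the protocol's T interval and signed-rank test while claiming consistency with Amendment 4, and its endpoint definition does not match its analysis. Drift remains visible in descriptive statistics but has no interval or test.

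On size: under a uniform +4% shift with SD 2%, the SAP's formal test passes about 94% of the time (81% at one-sided 2.5%), while the omitted interval would show the shift almost always. A shift of that size still lies inside the 7.5% limit, so a pass is not wrong as a statement about agreement. It is incomplete as a statement about drift.

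The figures rest on normal differences, on illustrative values of drift and SD, and on reading 0.075 as a percentage. The last is uncertain, because SAP 2.5 defines the change in TUV for Arms 1 and 2 as a plain difference. They apply to one arm of 38. SAP 4.1.1 lists TUV_global for Arms 2 and 3 only, so for the global measure that arm is Arm 2.

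**What to change.** 1. In SAP 4.2.2, restore the 95% T interval for the mean 180 minus 60 minute difference (A scans) and the signed-rank test, by arm. Do this for TUV_joint and, where it is defined, TUV_global, which under SAP 4.1.1 means Arm 2 here. Label the result as the estimate of systematic drift.
2. Keep the exact test of the fraction within 7.5% and the RMSD beside it as the agreement measures. State that an interval covering zero is not taken as proof of stability.
3. In SAP 4.1.2, replace the squared-difference definition with wording that matches the planned analyses.
4. Record which measure was used in interim analysis 3, and document the departure from the protocol with its reason.

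The cost is some SAP text and one more analysis of data already held. The stability statement may become less favourable if the interval shows a shift.

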8.3.4 ACR Response Criteria

Subjects in Arm 3 will be evaluated using the ACR Response Criteria ([Ward 2014](#)). ACR Response is derived from 6 possible parameters: swollen/tender joint count, patient assessment, physician assessment, pain scale, disability/functionality questionnaire, and acute phase reactant (ESR). Response is reported as percent (%) improvement from baseline to a later timepoint. In this case, a total of 3 timepoints will be evaluated per subject (Table 10).

Percent improvement is defined as a combination of reductions in swollen or tender joint counts as well as improvement in at least at least 3 of the other parameters (patient assessment, physician assessment, pain scale, disability/functionality questionnaire, and acute phase reactant [ESR]). An ACR20 indicates that 20% improvement is observed in tender or swollen joint counts as well as 20% improvement in at least 3 of the other 5 criteria. An ACR50 indicates that 50% improvement is observed in tender or swollen joint counts as well as 50% improvement in at least 3 of the other 5 criteria. An ACR70 indicates that 70% improvement is observed in tender or swollen joint counts as well as 20% improvement in at least 3 of the other 5 criteria. See [Appendix 7](#) for details.

Table 10 Timing of ACR Response Evaluations by Study Arm

Arm	Visit (Day)
1	Not performed
2	Not performed
	Visit 4 (5 ± 1 Weeks post-initiation of new anti-TNF α bDMARD)
3	Visit 6 (12 ± 1 Weeks post-initiation of new anti-TNF α bDMARD)
	Visit 8 (24 ± 1 Weeks post-initiation of new anti-TNF α bDMARD)

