Appendix 8 ACR Response Criteria

ACR Response Criteria

The ACR (American College of Rheumatology) Criteria is a standard criteria to measure the effectiveness of various arthritis medications or treatments in clinical trials for [Rheumatoid Arthritis](#). The ACR is used to maximally discriminate effective treatment from placebo treatment in clinical trials. The ACR criteria is indicated as ACR 20, ACR 50 or ACR 70.

The ACR is reported as % improvement, comparing disease activity at two discrete time points (usually baseline and post-baseline comparison).

- ACR20 is \geq 20% improvement
- ACR50 is \geq 50% improvement
 - ACR50 responders include ACR20 responders
- ACR70 is \geq 70% improvement
 - ACR70 responders include ACR20 & ACR50 responders

Definition

The ACR Criteria is a dichotomous variable with a positive (=responder) or negative (=non-responder) outcome.

The ACR Criteria measures improvement in tender or swollen joint counts in improvement in at least three of the following parameters:

1. patient assessment
2. physician assessment
3. pain scale
4. disability/functional questionnaire
5. acute phase reactant (ESR or CRP)

ACR 20 has a positive outcome if 20% improvement in tender or swollen joint counts were achieved as well as a 20% improvement in at least three of the other five criteria.

ACR 50 has a positive outcome if 50% improvement in tender or swollen joint counts were achieved as well as a 50% improvement in at least three of the other five criteria.

ACR 70 has a positive outcome if 70% improvement in tender or swollen joint counts were achieved as well as a 70% improvement in at least three of the other five criteria.

Courtesy of https://www.phusewiki.org/wiki/index.php?title=ACR_Response_Criteria

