The Kendall rank correlation between $\Delta\text{TUV}_{\text{global}}$ at 5 weeks, $\Delta\text{TUV}_{\text{global}}$ at 12 and 24 weeks with the component parameters of ΔCDAI_{12w} and ΔCDAI_{24w} will be computed and 95% confidence intervals for the values provided using Fisher's Z-transformation. This analysis will be repeated for the correlation between $\Delta\text{TUV}_{\text{global}}$ at 12 and 24 weeks with change in DAS28 and with ACR Response Criteria components at 12 weeks and 24 weeks (Note: the Kendall rank correlation analysis with DAS28 and ACR Response Criteria components at 5 weeks is a primary endpoint, as described above in Section 4.2.1). The marginal distributions of the variables will be characterized with the mean, standard deviation, and the number of data pairs.

Concordance of improvement classification for: 1) $\Delta\text{TUV}_{\text{global}[5w]}$ bucketing; 2) $\Delta\text{TUV}_{\text{global}[5w]}$; 3) $\Delta\text{TUV}_{\text{global}[5w]}$ bucketing with ACPA bucketing; 4) $\Delta\text{TUV}_{\text{global}[12w]}$ bucketing; 5) $\Delta\text{TUV}_{\text{global}[12w]}$; 6) $\Delta\text{TUV}_{\text{global}[12w]}$ bucketing with ACPA bucketing; and 7) ACPA bucketing alone with clinical criteria (ACR Response, CDAL, DAS28, and HAQ-DI) will be analyzed as follows.

ACR Response is derived through a combination of reductions from baseline in swollen or tender joint counts as well as improvement from baseline in at least at least 3 of the other parameters (patient assessment, physician assessment, pain scale, disability/functionality questionnaire, and acute phase reactant [ESR]). This study will evaluate the following three levels of ACR Response:

- ACR20: An ACR20 indicates that 20% improvement is observed in tender or swollen joint counts as well as 20% improvement in at least 3 of the other 5 criteria.
- ACR50: An ACR50 indicates that 50% improvement is observed in tender or swollen joint counts as well as 50% improvement in at least 3 of the other 5 criteria.
- ACR70: An ACR70 indicates that 70% improvement is observed in tender or swollen joint counts as well as 70% improvement in at least 3 of the other 5 criteria.

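### The ACR20/50/70 rule needs improvement in only one of the two joint counts, so a subject whose swollen joints worsen can be classed as an ACR responder at any level

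*SAP*

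**What the plan says.** The joint condition is worded the same way wherever ACR response is defined.

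- SAP 4.2.2, general sentence: "ACR Response is derived through a combination of reductions from baseline in swollen or tender joint counts".
- SAP 4.2.2, by level: "An ACR20 indicates that 20% improvement is observed in tender or swollen joint counts"; "An ACR50 indicates that 50% improvement is observed in tender or swollen joint counts"; "An ACR70 indicates that 70% improvement is observed in tender or swollen joint counts".
- Protocol 8.3.4: "Percent improvement is defined as a combination of reductions in swollen or tender joint counts".
- Protocol Appendix 8: "ACR 20 has a positive outcome if 20% improvement in tender or swollen joint counts were achieved".

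Each level also needs improvement in at least three of five other items: patient global, physician global, pain, HAQ-DI and acute-phase reactant. No section requires both counts to improve, and none disqualifies a subject whose other count gets worse.

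The Protocol applies the rule to the whole arm: "Subjects in Arm 3 will be evaluated using the ACR Response Criteria". The SAP lists as a secondary variable "ACR Response Criteria at 12 and 24 weeks (Arm 3 only". SAP 4.2.2 then gives each subject a yes or no at each level and cross-tabulates that status against the TUV and ACPA predictions to obtain PPV, NPV and overall accuracy.

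**The concern.** Tender and swollen counts are recorded separately, so a programmer can code the *or* literally. Tenderness, patient global, pain and HAQ-DI can then satisfy any response level with no improvement in swelling, physician global or ESR. Protocol 8.3.5.6 already anticipates pain of another origin, because it collects the Widespread Pain Index to evaluate central pain.

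ACR status is one of the yardsticks by which the TUV algorithms are judged. A responder label that can coexist with growing swelling makes that yardstick hard to interpret. Arm 3 is small enough for a few such labels to change the reported predictive values, and the footnote to the Table 44 shell attaches p-values to PPV and NPV against a null of 0.6.

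**Working it through.** **Inputs.** The joint rule and the three-of-five rule come from SAP 4.2.2. The CDAI, DAS28 and HAQ-DI improvement rules are in the same section. CDAI is the sum of tender count, swollen count, patient global and physician global (Protocol 8.3.3). The DAS28 formula is in Protocol 8.3.2. Arm 3 has 29 evaluable subjects (SAP 1.3). No planned figure depends on the ACR joint rule, so there is none to reproduce.

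**Step 1: apply the rule to constructed subjects.** All values below are invented for illustration.

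| Item | Baseline | ACR20 case | ACR50 case | ACR70 case |
|---|---|---|---|---|
| Tender joints | 10 | 8 (−20%) | 5 (−50%) | 3 (−70%) |
| Swollen joints | 6 | 9 (+50%) | 9 (+50%) | 9 (+50%) |
| Patient global | 6 | 4.5 (−25%) | 3 (−50%) | 1.5 (−75%) |
| Pain | 60 | 45 (−25%) | 30 (−50%) | 18 (−70%) |
| HAQ-DI | 1.5 | 1.2 (−20%) | 0.75 (−50%) | 0.375 (−75%) |
| Physician global | 6 | 6 | 6 | 6 |
| ESR | 40 | 40 | 40 | 40 |
| Rule as written | | responder | responder | responder |
| Both counts required | | non-responder | non-responder | non-responder |

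In each case one joint count and three of the five other items reach the threshold, so the rule is met.

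**Step 2: compare with the SAP's other criteria for the same subjects.**

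- CDAI: baseline 10 + 6 + 6 + 6 = 28. Follow-up is 8 + 9 + 4.5 + 6 = 27.5, 5 + 9 + 3 + 6 = 23, and 3 + 9 + 1.5 + 6 = 19.5. The falls are 0.5, 5 and 8.5. From a baseline above 22 the SAP needs a fall of more than 12, so all three are not improved.
- DAS28, taking its VAS equal to the pain value (an assumption) and ESR unchanged: the fall is 0.56(√10 − √TJC) + 0.28(√6 − √9) + 0.014 × (VAS fall). This gives 0.187 − 0.154 + 0.210 = 0.243, then 0.519 − 0.154 + 0.420 = 0.785, then 0.801 − 0.154 + 0.588 = 1.235. Against the threshold of more than 1.2, only the ACR70 case is improved.
- HAQ-DI: the falls are 0.3, 0.75 and 1.125. All reach 0.22, so all are improved.

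**Step 3: effect on PPV and NPV.** Assume 15 subjects predicted improved and 14 not (total 29), with A = 11, B = 4, C = 4, D = 10 in the SAP's notation. Requiring both counts can only move responders to non-responders: A to B (PPV falls) or C to D (NPV rises).

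| Reclassified | PPV (exact 95% CI) | NPV (exact 95% CI) |
|---|---|---|
| 0 | 11/15 = 0.733 (0.449–0.922) | 10/14 = 0.714 (0.419–0.916) |
| 1 | 10/15 = 0.667 (0.384–0.882) | 11/14 = 0.786 (0.492–0.953) |
| 2 | 9/15 = 0.600 (0.323–0.837) | 12/14 = 0.857 (0.572–0.982) |

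One subject is worth 1/15 = 6.7 points of PPV or 1/14 = 7.1 points of NPV.

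**Step 4: where the rule is used.**

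- Protocol 9.3 and 9.5.3.3 include the correlation of the week-5 TUV change with overall ACR response at Weeks 12 and 24 in the Arm 3 primary endpoint. That response is defined by this rule.
- In the SAP the rule drives Table 42, Figures 1 to 3, and three of the six parts of each of Tables 44 to 65: 22 tables × 3 = 66 cross-classifications.
- SAP 4.1.1 and 4.2.1 define the primary Kendall analyses on CDAI, DAS28 and the individual ACR components. The footnote to the Table 19 shell lists tender and swollen counts separately. The *or* does not enter them.

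**The case against.** The documents are consistent. Every definition says *or*, so there is no contradiction to resolve, and they contain no source showing that *both* is the correct rule. Protocol 8.3.4 also treats the joint count as one of six parameters, so the wording may be loose rather than chosen. This stands in part: the case for change rests on what the rule does, not on a conflict or a published standard, and the sponsor should confirm what was meant.

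A worsening swollen count would also remain visible elsewhere. CDAI sums both counts, components are summarised separately, and CDAI, DAS28 and HAQ-DI are parallel criteria in the same tables. That is true, but it does not correct the ACR parts. In the constructed ACR70 case DAS28 and HAQ-DI side with the responder label and only CDAI does not.

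A reader might infer that the rule scores correct TUV predictions as errors, because TUV would rise with swelling. The documents do not support that. Protocol 1.2.4.1 reports poor agreement between tilmanocept localization and swollen or tender joints in a prior subcutaneous study, and the SAP's reference is the clinical criterion, not the swollen count.

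The timing objection also stands. SAP 2.4 says Interim Analysis 3 has been performed and was used to optimise the TUV metric, so a changed responder definition needs to be documented and shown alongside the existing one.

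**Conclusion.** The point holds as a flaw in a stated definition. Followed literally, the rule can label a subject with a 50% rise in swollen joints an ACR20, ACR50 or ACR70 responder, and no other sentence prevents it. The reach is the Protocol's overall ACR correlation and the SAP's secondary ACR outputs.

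Three stronger readings should be resisted.

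- That the SAP's primary Arm 3 analyses are compromised: they use separate components and are untouched.
- That the resulting rates are not comparable with ACR20/50/70 in other trials: this would need outside sources.
- That a known share of responders is misclassified: the documents give no improvement rates or correlation between the counts. Failing the threshold on one count is not the same as worsening, and the three-of-five condition would remove some subjects.

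The only size offered is the sensitivity per subject, about 7 points of PPV or NPV, and it rests on the assumed 15/14 split.

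**What to change.** Before database lock:

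- Change the joint condition to require the stated improvement in both the tender and the swollen joint count at 20%, 50% and 70%.
- Make the same change in SAP 4.2.2 (the general sentence and all three levels), Protocol 8.3.4 and Appendix 8.
- State how a zero baseline count is handled, since percent improvement is then undefined.
- Derive the status from the component values already in Listings 18 and 28.
- Report the *or* version as a sensitivity analysis, because Interim Analysis 3 has already been performed. Choosing between the two after seeing PPV and NPV would be a post hoc choice of reference standard.
- In the same edit, reconcile the ACR70 sentence in Protocol 8.3.4, which asks for 20% in the other items where Appendix 8 and the SAP ask for 70%. That is a separate inconsistency.

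No new data are needed. The costs are a documented amendment (Protocol 3.2 requires one for changes that are not purely administrative), a SAP revision, a small change to the derivation code, the additional sensitivity output, and ACR response rates that can only stay the same or fall.
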